2.3.2 Demographic variables and other baseline characteristics

Demographic variables and other baseline characteristics including previous migraine treatments will be summarized for each randomized treatment group and for all participants (total) using RAS.

At baseline (end of the baseline period; see Section 2.1.1.2, baseline definition), the following demographic and baseline characteristics will be summarized:

- Categorical variables:
 - o Sex
 - o Ethnicity
 - o Race
 - Acute headache medication (none, migraine-specific/non migraine-specific) during baseline phase
 - Strata*: Prior prophylactic migraine medication treatment failure (prior prophylactic migraine treatment failure, due to efficacy or tolerability, vs no prior prophylactic migraine treatment failure).
 - Aura status during baseline: Migraine with aura (ever experienced a migraine with aura during the baseline period), migraine without aura (never experienced any migraine with aura during the baseline period)
 - Number of prior prophylactic treatment failures based on the treatment category -(0, 1, 2, 3, 4, >4)
 - Beck Depression Inventory (BDI)-II total score severity grade (minimal depression (0-13), mild depression (14-19))
- Continuous variables:
 - o Age
 - Height (cm)
 - Weight (kg)

- o Body Mass Index (BMI, kg/m2)
- Age at onset of migraine (years)
- o Disease duration of migraine with or without aura (years)
- Monthly migraine days during baseline phase
- Monthly migraine attacks during baseline phase
- Monthly headache days during baseline phase
- Monthly acute migraine-specific medication use in days during baseline phase
- Monthly acute headache medication use in days during baseline phase

*value used for randomization.

Descriptive statistics (mean, median, standard deviation, minimum, and maximum) will be presented for continuous variables for each randomized treatment group and for all participants (total) using RAS. The number and percentage of participants in each category will be presented for categorical variables for each treatment group and all participants (total).

If multiple races have been reported for a subject, the subject will be categorized as multiple and in each selected race category.

The number of patients per country for each treatment group will be presented.

Summary of prior migraine prophylactic treatment and reasons for discontinuation will be presented by treatment group and by medication category (as defined in section 2.1.1.4).

Subject demographics and baseline characteristics including stratification factor and ethnicity will be listed by treatment.

Subject disease history characteristics (listed below) collected on the "Headache and Migraine Frequency History" CRF page will be listed by treatment:

- Age at onset of migraine (years)
- Disease duration of migraine with or without aura (years) derived.
- Frequency of migraines over the past 3 months (average days per month subject had migraines)

2.3.3 Frequency of headache (migraine and non-migraine) over the past 3 months (average days per month subject had headache)Medical history

Relevant medical history/current medical conditions present before signing the Informed consent will be recorded on the 'Medical History' CRF page.

Any condition entered will be coded using the latest version Medical Dictionary for Regulatory Activities (MedDRA) prior to database lock and summarized by primary system organ class (SOC) and preferred term (PT) for each randomized treatment group and for all participants (total) using RAS (randomized analysis set). The SOCs will be presented in alphabetical order. Preferred terms will be ordered within each SOC by decreasing order of frequency in the AMG334 140mg arm.

Relevant medical history and current medical conditions will be listed by treatment.

2.4 Treatments (study treatment, rescue medication, concomitant therapies, compliance)

2.4.1 Study treatment / compliance

Exposure will be calculated for patients in the SAF and is defined as the number of investigational product doses received (planned to be 2 injections per dose) by patient.

Descriptive statistics will be produced to describe the exposure to investigational product by treatment group. The proportion of patients who received 1, 2 or 3 doses will be provided.

A listing with the investigational drug (AMG 334 or placebo) injections administered will be provided.

The duration of exposure since first injection will be summarized descriptively by treatment group.

At each visit, the number and percentage of patients receiving an investigational drug (AMG 334 or placebo) dose will be summarized by treatment group. Additionally, the number and percentage of patients with dose change and reason for dose change will be summarized by treatment group and by visit.

2.4.2 **Prior**, concomitant and post therapies

The number and percentage of participants receiving concomitant (during the double-blind treatment period) medications, and significant non-drug therapy will be summarized by SOC, preferred term (coded by WHO Anatomic Therapeutic Chemical classification [ATC]) and by treatment arm, and be listed. The use of concomitant medications and significant non-drug therapy during the follow-up period will be summarized in the same way, in a separate table, but will be listed in the same listing. Medications and significant non-drug therapies prior to start of study drug by treatment will only be listed.

Use of other non-pharmacological treatments and traditional techniques (such as acupuncture, traditional and herbal medicine) during the baseline phase and the DBTP will be summarized by category of medication for each treatment group in a separate table.

Use of acute headache medication during the baseline phase and the DBTP will be summarized by category of medication for each treatment group.

2.4.3 **Prohibited treatment**

Analysis of concomitant medications, procedures that are prohibited as per protocol (see protocol Section 5.5.8) and given during the conduct of the study will be addressed by the currently planned outputs for the protocol deviations.

No separate outputs will be produced related specifically to prohibited medications.

2.5 Analysis of the primary objective

2.5.1 **Primary endpoint**

The primary efficacy variable is the change from baseline in monthly migraine days in the last month (Month 3) of the DBTP.

Analysis of the primary endpoint will utilize the FAS. Subjects will be analyzed according to their randomized treatment group regardless of the actual treatment received during the study.

2.5.2 Statistical hypothesis, model, and method of analysis

The primary efficacy endpoint variable will be analyzed using a linear mixed effects repeated measures model based on observed monthly data during the DBTP and pairwise comparisons (AMG 334 140mg vs. placebo, and AMG 334 70mg vs. placebo) will be conducted.

The model will include treatment, scheduled visit, treatment by visit interaction, and the stratification variable and baseline values as covariates. If applicable, in the repeated statement, an unstructured covariance structure is assumed. Least squares means (LSMs) for each treatment group, difference of LSMs compared to placebo group and the associated 95% confidence interval of the differences, as well as the nominal two-sided p-values, will be tabulated by visit and treatment.

The primary endpoint of the study will be first tested for each of AMG 334 70 mg and 140 mg compared to placebo, respectively.

- Null Hypothesis: In subject with episodic migraine, the AMG 334 treatment group is the same as placebo, in terms of the reduction from baseline in mean monthly migraine days in the last month (month 3) of the DBTP
- Alternative Hypothesis: In subject with episodic migraine, the AMG 334 treatment group is different from placebo, in terms of the reduction from baseline in mean monthly migraine days in the last month (month 3) of the DBTP

A hierarchical gate-keeping procedure and the Hochberg method will be used to maintain the overall 2-sided study-wise type I error rate at 0.05 for the primary endpoint and secondary efficacy endpoints. See further details in protocol Section 9.5 and Section 2.6.2 of this document.

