# 3 Investigational plan

### 3.1 Study design

This study uses a single-cohort, 3-treatment arm, randomized (2:3:3 [140 mg: 70 mg: placebo]), double-blind study design in adult patients with episodic migraine. A screening period of 2 weeks will be used to assess initial eligibility, followed by a 4-week baseline period (the maximum duration for the baseline period is 35 days), during which diary compliance and headache frequency will be assessed for a final eligibility assessment prior to randomization and dosing. After randomization/Day 1, visits will occur at four week intervals until Week 12, which is the End of Treatment visit, Last Patient Last Treatment (LPLT). The final visit, Last Patient Last Visit (LPLV), a Safety Follow-Up visit, will occur 12 weeks later, at Week 24.

A blinded interim analysis after approximately 50% patients have completed the DBTP will be conducted to re-estimate the sample size by providing information on the variance for this trial relative to the planning assumptions to account for potential higher variability in Asian countries/new sites.

End of Trial will occur when the last patient completes their last visit (LPLV) of the study.

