# 5.3 Treatment assignment and randomization

At Visit 110 (Day 1), all eligible patients/subjects will be randomized via Interactive Response Technology (IRT) to one of the treatment arms. The investigator or his/her delegate will contact the IRT after confirming that the patient fulfills all the inclusion/exclusion criteria. The IRT will assign a randomization number to the patient, which will be used to link the patient to a treatment arm and will specify a unique medication number for the first package of study drug to be dispensed to the patient. The randomization number will not be communicated to the caller.

The randomization numbers will be generated using the following procedure to ensure that treatment assignment is unbiased and concealed from patients/subjects and investigator staff. A patient randomization list will be produced by the IRT provider using a validated system that automates the random assignment of patient numbers to randomization numbers. These randomization numbers are linked to the different treatment arms, which in turn are linked to medication numbers. A separate medication list will be produced by or under the responsibility of Novartis Drug Supply Management using a validated system that automates the random assignment of medication numbers to packs containing the investigational drug(s).

Randomization will be stratified by prior prophylactic migraine treatment failure according to the planned randomization ratio within each stratum. The randomization scheme for patients/subjects will be reviewed and approved by a member of the Randomization Group.

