2.2.1 Subgroup of interest

The primary and secondary efficacy endpoints will be analyzed at week 12 for the following subgroups that are defined by categorical variables at baseline:

- prior prophylactic migraine medication treatment failure (prior prophylactic migraine treatment failure, due to efficacy or tolerability, vs no prior prophylactic migraine treatment failure)
- Number of prior prophylactic migraine treatment failure medications: $\geq 2,<2$
- Age (< median vs \geq median)
- BMI (< median vs \geq median)
- Sex (Male vs Female)
- Region (see appendix E):
 - Asia (excluding India, Taiwan, Korea)
 - o India
 - o Taiwan
 - o Korea
 - o Others

The effect of other baseline variables, maybe investigated with respect to the primary and secondary efficacy analyses if, upon clinical review, differences between treatment groups are deemed clinically meaningful.

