2.6.2 Statistical hypothesis, model, and method of analysis

Analysis of secondary efficacy endpoints will utilize the FAS except for the analysis of change from baseline in monthly acute migraine-specific treatment days in Month 3 of the DBTP, which will be conducted based on the subgroup of patients who used acute migraine-specific medication during baseline. Subjects will be analyzed according to their randomized treatment group regardless of the actual treatment received during the study.

The above continuous change from baseline efficacy endpoints will be analyzed using a linear mixed effects repeated measures model with treatment group, baseline value, stratification factor, scheduled visit, and the interaction of treatment group with scheduled visit, without any imputation for missing data. If applicable, in the repeated statement, an unstructured covariance matrix will be used.

The dichotomous endpoint (Proportion of patients who achieve at least a 50% reduction from baseline in monthly migraine days in the last month of DBTP) will be analyzed based on Cochran-Mantel-Haenszel (CMH) test after patients who have missing monthly migraine day data at Month 3 of the DBTP imputed as non-responders.

The description of the models can be found in Section 5.4.

In all cases, estimates (difference or odds ratio) of treatment group compared to placebo group with associated nominal 95% confidence intervals and nominal two-sided p-values will be provided.

A hierarchical gate-keeping procedure and the Hochberg method will be used to maintain the overall 2-sided study-wise type I error rate at 0.05 for the primary endpoint and secondary efficacy endpoints. The primary endpoint, the change from baseline in monthly migraine days

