2.6.5 Supplementary analyses

2.6.5.1 Subgroup analyses

The primary and secondary efficacy endpoints will be analyzed at week 12 for the following subgroups that are defined by categorical variables at baseline:

- Prior prophylactic migraine medication treatment failure (prior prophylactic migraine treatment failure, due to efficacy or tolerability, vs no prior prophylactic migraine treatment failure)
- Number of prior prophylactic migraine treatment failure medications: >=2,<2
- Age (< median vs \geq median)
- BMI (< median vs \geq median)
- Sex (Male vs Female)
- Region:
 - Asia (excluding India, Taiwan, Korea)
 - o India
 - o Taiwan
 - o Korea
 - o Others

The effect of other baseline variables, maybe investigated with respect to the primary and secondary efficacy analyses if, upon clinical review, differences between treatment groups are deemed clinically meaningful.

The purpose of the subgroup analyses is to explore if the treatment effect varies across subgroups of interest. Subgroup analyses are performed for primary and secondary efficacy endpoints using the same method as primary analysis method but performed within each subgroup of interest. The treatment difference (or odds ratio) with associated 95% confidence intervals and p-values will be reported within each subgroup.

Note: if the subgroup is the stratification factor (Prior prophylactic migraine medication treatment failure) then the stratification factor will not be included in the model.

The heterogeneity of the treatment effect across the subgroups will be evaluated for the primary and secondary endpoints by examining the treatment by subgroup interaction at primary time point (Week 12) and a p-value will be presented. For continuous endpoints, the primary analysis model with the addition of subgroup and treatment group by subgroup interaction as two additional effects will be used. For endpoint based on proportions, a logistic regression model that includes treatment group, stratification factor, baseline value, subgroup and treatment group by subgroup interaction will be used.

If the value of the group variable cannot be determined, the subject will be excluded from the corresponding subgroup analysis. For each subgroup analysis, if, in any treatment group, the number of subjects is less than 10 for a subgroup, then only summary statistics will be performed.

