2.13 Interim analysis

To account for potential larger than expected variability during the DBTP of the trial, a blinded interim assessment is planned after about 50% of subjects finish their DBTP or early withdraw. Only the standard deviation of the primary variable, change from baseline in monthly migraine days in month 3, based on pooled (blinded) data from all subjects who had the opportunity to complete the week 12 assessment in the trial, will be estimated. The sample size will be increased appropriately, up to an additional 200 subjects, only if the standard deviation is larger than 5.

The type I error of the primary analysis will be maintained, as the treatment assignment will remain blinded and there is no intention to stop the study early due to efficacy.

3 Sample size calculation

A treatment difference of -1.79 days for change from baseline in monthly migraine days in Month 3 between AMG 334 140mg and placebo was observed in study 20120296 (STRIVE).

A treatment difference of -1.16 days for change from baseline in monthly migraine days in Month 3 between AMG 334 70mg and placebo was observed based on pooled analysis on the combined data from studies 20120296, 20120297, and 20120178.

Assuming a treatment effect similar to the effect observed in previous studies with AMG 334 in episodic migraine, the treatment difference in terms of change from baseline on monthly migraine days during week 9-12 (primary variable) for erenumab 140mg vs. placebo and 70mg vs. placebo is assumed at -1.5 days and -1.1 days, respectively. The common standard deviation of the primary variable is assumed at 4. Given a 2:3:3 randomization ratio among erenumab 140mg, 70mg, and placebo, a total of 880 subjects (including 10% drop out rate) would enable

| Novartis | For business use only | Page 48 |
|-----------------|-----------------------|--------------|
| SAP Amendment 1 | | CAMG334A2302 |

both doses to achieve higher than 90% power under overall 0.05 full alpha level to detect the designed treatment difference. In addition, the sample size will also ensure the trial to have adequate power to detect treatment difference under initial 2-sided 0.025 alpha level assigned to each dose (equally split between the erenumab two doses).

4 Change to protocol specified analyses

The following analyses will be performed and are not planned in the protocol

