5.4.2 Secondary analysis

5.4.2.1 Method I

The first secondary analyses will compare the 50% response rate, which is defined as the proportion of patients who achieve at least a 50% reduction from baseline in monthly migraine days in the last month (month 3) of the Double-Blind Treatment Period, for each of AMG 334 70 mg and 140 mg compared to placebo, respectively.

- Null Hypothesis: In subject with episodic migraine, the AMG 334 treatment group is inferior or the same as placebo, in terms of the proportion of patients who achieve at least a 50% reduction from baseline in monthly migraine days in the last month (month 3) of the Double-Blind Treatment Period
- Alternative Hypothesis : In subject with episodic migraine, the AMG 334 treatment group is superior to placebo, in terms of the proportion of patients who achieve at least a 50% reduction from baseline in monthly migraine days in the last month (month 3) of the Double-Blind Treatment Period

More precisely, the null hypothesis stating that the odds ratio between the two treatment arms less than or equal to 1 will be tested against the one-sided alternative.

H₀:
$$\theta_1 \leq 1$$
 vs H₁: $\theta_1 > 1$

where θ_1 is the odds ratio of active over corresponding placebo.

Test statistic:

After the missing data are imputed as non-response, a Cochran-Mantel-Haenszel (CMH) test stratified by the randomization strata will be used under a significance level of alpha/2, one-sided (alpha, two-sided; See further details in protocol Section 9.5 and Section 2.6.2 of this document for the value of alpha) to evaluate the association between the 50% responder rate and the treatment. The estimated common odds ratio, confidence intervals and p-values will be reported.

Sensitivity analysis:

• Logistic regression analysis will be used to test the superiority of AMG334 arm in the 50% response rate after the missing data are imputed as non-response. Baseline migraine days will be used as a covariate along with treatment and stratification factor as fixed effects in the model.

The odds ratio of treatment group compared to placebo group with associated 95% confidence intervals and 2-sided p-values will be provided.

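### Region is not a covariate in the primary and continuous secondary models, so some precision may be given up; validity and the stated power are not affected.

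*SAP*

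**What the plan says.** SAP 2.5.2 lists the terms of the primary repeated-measures model: "The model will include treatment, scheduled visit, treatment by visit interaction, and the stratification variable and baseline values as covariates". SAP 5.4.1 and Protocol 9.4.2 give the same terms. For the continuous secondary endpoints, SAP 2.6.2 specifies a "linear mixed effects repeated measures model with treatment group, baseline value, stratification factor, scheduled visit, and the interaction of treatment group with scheduled visit", repeated in Table 2-4 and 5.4.2.2. The ANCOVA sensitivity analysis (SAP 2.5.4) uses treatment, stratification factor and baseline. For the responder endpoint, "a Cochran-Mantel-Haenszel (CMH) test stratified by the randomization strata will be used" (SAP 5.4.2.1). None of these contains region, country or centre.

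Region is not a randomisation factor either: "Randomization will be stratified by prior prophylactic migraine treatment failure according to the planned randomization ratio within each stratum" (Protocol 5.3).

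Region is nevertheless a defined baseline variable. SAP Table 5-6 has five levels: India, Taiwan, Korea, other Asia, and a remaining group of Lebanon, Argentina and Mexico. It is a planned subgroup, and for the interaction test on continuous endpoints "the primary analysis model with the addition of subgroup and treatment group by subgroup interaction as two additional effects will be used" (SAP 2.6.5.1). Region therefore already enters one planned model as a main effect.

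On variability, Protocol 3.1 explains that the blinded interim look is there "to account for potential higher variability in Asian countries/new sites". The rule is: "The sample size will be increased appropriately, up to an additional 200 subjects, only if the standard deviation is larger than 5" (SAP 2.13).

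**The concern.** The trial's purpose is to obtain data from regions under-represented in earlier studies (Protocol 1.2). The protocol says that standard of care varies markedly by geography (1.1, 3.4) and that non-traditional therapies are very common in Asia (1.1). It allows such therapies during the trial if they are stable (5.5.8). It is therefore plausible that mean change in monthly migraine days differs between regions for reasons that baseline and prior-treatment failure do not capture.

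Any such difference stays in the residual of the planned models. Chance imbalance of arms across regions is also left unadjusted, because region is neither stratified on nor modelled. The result would be wider confidence intervals than necessary for both doses. The 70 mg comparison has the smaller assumed effect and so the least power to spare, especially at its starting level of two-sided 0.025.

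**Working it through.** **Inputs from the documents** (Protocol 9.8, SAP 3, SAP 1.1): differences of 1.5 days (140 mg) and 1.1 days (70 mg); SD 4; allocation 220 / 330 / 330; 10% dropout, leaving 198 / 297 / 297 evaluable.

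**Assumptions.** R² is the share of residual variance at Month 3 that the region term removes after baseline and stratum. It is not in the documents; 0 to 10% is assumed. The planning SD is treated as the residual SD.

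**Formula.** Power = Φ(δ/SE − z), with SE = SD × √(1/n₁ + 1/n₂) and z = 1.960 at two-sided 0.05 or 2.241 at two-sided 0.025. With region fitted, SD becomes SD × √(1 − R²).

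**Step 1: the plan's own figure.**
- 70 mg: SE = 4 × √(2/297) = 0.328; 1.1/0.328 = 3.351. Power is Φ(3.351 − 1.960) = 91.8% at 0.05 and Φ(3.351 − 2.241) = 86.6% at 0.025.
- 140 mg: SE = 4 × √(1/297 + 1/198) = 0.367; 1.5/0.367 = 4.087. Power is 98.3% at 0.05 and 96.8% at 0.025.

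The claim of more than 90% for both doses at 0.05 reproduces without region. At 0.025 the documents claim only adequate power.

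**Step 2: 70 mg with region added, SD 4.** Equivalent extra patients = 880 × (1/(1 − R²) − 1). Implied between-region SD of mean change = 4 × √R².

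| R² | SE | Power at 0.025 | Power at 0.05 | Equivalent extra patients | Between-region SD (days) |
|---|---|---|---|---|---|
| 0 | 0.328 | 86.6% | 91.8% | 0 | 0 |
| 2% | 0.325 | 87.4% | 92.3% | 18 | 0.57 |
| 5% | 0.320 | 88.4% | 93.0% | 46 | 0.89 |
| 10% | 0.311 | 90.2% | 94.2% | 98 | 1.26 |

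The SE falls by 1 − √(1 − R²), that is 1.0%, 2.5% and 5.1%.

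**Step 3: larger SD, 70 mg at 0.025, 297 per arm.**
- SD 4.5, below the interim trigger: 77.0% with no region effect, 79.2% at R² 5%, 81.6% at 10%.
- SD 5, with no sample-size increase: 67.0%, 69.5% and 72.1%.

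**Step 4: cost if region explains nothing.** Five levels use four degrees of freedom. With 792 evaluable patients and five parameters already fitted, the SE rises by a factor of √(787/783) = 1.0026, about 0.25%.

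**The case against.** The case for leaving the models alone has real substance.

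- **No loss is demonstrated.** Precision improves only if regional means differ after adjustment for baseline and stratum, and the documents give no figure for that. R² of 10% would need a between-region SD of about 1.3 days, more than the assumed 70 mg effect of 1.1 days. This stands: the gain is possible, not established.
- **The stated worry is about variance.** A reader might infer that the plan fears regional variability and then ignores it in the model. The documents do not support that. The worry is a higher SD in Asian countries and new sites, and the blinded SD check answers it. A region main effect removes shifts between regional means; it cannot shrink a larger SD within a region. The two overlap only in that the pooled interim SD contains any between-region shift as well.
- **Region is not ignored.** Subgroup estimates and an interaction test by region are planned. They do not change the precision of the confirmatory comparisons, however.
- **The 0.025 figure is the least favourable one.** Under the alpha transfer described in SAP 2.6.2, 70 mg can be re-tested at 0.05 if 140 mg succeeds on the primary and all secondary endpoints. It can be tested at 0.025 + 0.0125 = 0.0375 if 140 mg succeeds on the primary endpoint but not on all secondary endpoints. Power without region is then 91.8% or 89.8%. This stands.
- **The responder analysis is different.** Adding region to the logistic regression changes the conditional odds ratio being estimated, so the linear-model precision argument does not carry over. This stands too.

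What remains is that region is a plausible prognostic factor on the protocol's own account, is already defined, and costs almost nothing to include.

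**Conclusion.** This is an efficiency improvement worth making, not an error in the plan. Precision may be lost on the primary and continuous secondary endpoints. The size depends on an unknown share of variance: for an assumed 0 to 10%, 70 mg power at 0.025 gains between 0 and about 3.5 percentage points (86.6% to 90.2%), and the SE falls by at most about 5%. At an assumed 2% the gain is under one point.

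A reader might conclude that the omission biases the treatment comparison, inflates type I error or leaves the trial underpowered. None of these follows. Region is not a randomisation factor, so the analysis matches the design. The usual confidence interval already allows for chance imbalance. The stated power of more than 90% at 0.05 holds without region for both doses.

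The figures rest on the planning effect sizes, 10% dropout, a normal approximation and the planning SD taken as the residual SD.

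**What to change.** Before unblinding:

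- Add region (the five levels of SAP Table 5-6) as a fixed effect to the primary repeated-measures model (SAP 2.5.2, 5.4.1) and the continuous secondary models (SAP 2.6.2, Table 2-4, 5.4.2.2).
- Carry it into the ANCOVA sensitivity analysis (SAP 2.5.4) and the multiple-imputation models (SAP 5.1.5.3.2, whose variable list has race group but not region), so that they stay aligned with the primary model.
- Drop it from models fitted within a region subgroup, as SAP 2.6.5.1 already does for the stratification factor.
- Leave the CMH test on the randomisation stratum, and claim no precision gain for the responder logistic regression.
- Record the change in SAP Section 4 as a departure from Protocol 9.4.2.

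No new data are needed. The statistical cost is four degrees of freedom, about 0.25% in SE if region explains nothing. The editorial cost is consistent wording across the sections listed. If the sponsor prefers to keep the protocol's model as primary, a pre-specified region-adjusted sensitivity analysis is the minimum; none is planned now.
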